APPENDIX

ENGLISH

**EORTC QLQ-C30 (version 3)**

We are interested in some things about you and your health. Please answer all of the questions yourself by circling the number that best applies to you. There are no "right" or "wrong" answers. The information that you provide will remain strictly confidential.

Please fill in your initials:

aaaa

Your birthdate (Day, Month, Year):

bbdbcccd

Today's date (Day, Month, Year):

31 bdbdbcccd

	Not at All	A Little	Quite a Bit	Very Much
1. Do you have any trouble doing strenuous activities, like carrying a heavy shopping bag or a suitcase?	1	2	3	4
2. Do you have any trouble taking a long walk?	1	2	3	4
3. Do you have any trouble taking a short walk outside of the house?	1	2	3	4
4. Do you need to stay in bed or a chair during the day?	1	2	3	4
5. Do you need help with eating, dressing, washing yourself or using the toilet?	1	2	3	4
During the past week:				
6. Were you limited in doing either your work or other daily activities?	1	2	3	4
7. Were you limited in pursuing your hobbies or other leisure time activities?	1	2	3	4
8. Were you short of breath?	1	2	3	4
9. Have you had pain?	1	2	3	4
10. Did you need to rest?	1	2	3	4
11. Have you had trouble sleeping?	1	2	3	4
12. Have you felt weak?	1	2	3	4
13. Have you lacked appetite?	1	2	3	4
14. Have you felt nauseated?	1	2	3	4
15. Have you vomited?	1	2	3	4
16. Have you been constipated?	1	2	3	4

Please go on to the next page

ENGLISH

During the past week:

	Not at All	A Little	Quite a Bit	Very Much
17. Have you had diarrhea?	1	2	3	4
18. Were you tired?	1	2	3	4
19. Did pain interfere with your daily activities?	1	2	3	4
20. Have you had difficulty in concentrating on things, like reading a newspaper or watching television?	1	2	3	4
21. Did you feel tense?	1	2	3	4
22. Did you worry?	1	2	3	4
23. Did you feel irritable?	1	2	3	4
24. Did you feel depressed?	1	2	3	4
25. Have you had difficulty remembering things?	1	2	3	4
26. Has your physical condition or medical treatment interfered with your family life?	1	2	3	4
27. Has your physical condition or medical treatment interfered with your social activities?	1	2	3	4
28. Has your physical condition or medical treatment caused you financial difficulties?	1	2	3	4

For the following questions please circle the number between 1 and 7 that best applies to you29. How would you rate your overall health during the past week?

1 2 3 4 5 6 7

Very poor

Excellent

30. How would you rate your overall quality of life during the past week?

1 2 3 4 5 6 7

Very poor

Excellent

EORTC QLQ-30 Scoring Procedure

The European Organization for Research and Treatment of Cancer (EORTC) developed an integrated modular approach for evaluating quality of life (QoL) in patients participating in cancer clinical trials. The EORTC QLQ-C30 (version 3.0) questionnaire consists of three scales; functional scale, symptom scale, and a global QoL scale.

Inclusion criteria no 2 of the study protocol requires that the subjects need to show “Evidence of reduced function or presence of cancer related symptoms as determined by EORTC QLQ-C30”. In order to determine eligibility, it is necessary to calculate the functional and symptom scores at the screening visit. The following steps describe the scoring procedure and the algorithm for computing the item level score (1). Please refer to table A1 for a list of questions that are included in the specific functional and symptom scales.

Calculate Raw Score (RS):

There are four response categories for each item (question). Based on the response to a given question, please assign a numeric value to the individual item; i.e. Not at All =1, A Little =2, Quite a Bit =3, and Very Much =4.

Then calculate raw score for a particular scale by taking the average of the individual item scores $[(I_1+I_2+I_3...I_n)/n]$.

For example, Fatigue is composed of three items, question 10, 12, and 18. So the raw score will be (response to Q10+response to Q12+ response to Q18)/3.

Linear Transformation:

All the scales need to be transformed to a linear scale and the final score should range from 0 to 100. Use the following formula to apply linear transformation and obtain the final score (S).

$$S = \{1 - ((RS - 1) / \text{range})\} \times 100$$

Range: range is the difference between maximum and minimum possible scores. With 4 response categories in each item, the maximum and minimum scores can take a value of 4 to 1. Hence the **Range will be 3 for all the functional and symptom scales.**

Screenshot showing a sample EORTC QLQ-C30 questionnaire from the CRF page.

EORTC QUESTIONNAIRE

Was EORTC questionnaire administered?

YES
 NO

	Not at All	A Little	Quite a Bit	Very Much	
9. During the past week, have you had pain?					Fatigue
10. During the past week, did you need to rest?					
11. During the past week, have you had trouble sleeping?					
12. During the past week, have you felt weak?					
13. During the past week, have you lacked appetite?					
14. During the past week, have you felt nauseated?					
15. During the past week, have you vomited?					
16. During the past week, have you been constipated?					
17. During the past week, have you had diarrhea?					
18. During the past week, were you tired?					
19. During the past week, did pain interfere with your daily activities?					
20. During the past week, have you had difficulty concentrating on things, like reading a newspaper or watching television?					Emotional Function
21. During the past week, did you feel tense?					
22. During the past week, did you worry?					
23. During the past week, did you feel irritable?					

Subject Withdrew Consent	XX (XX)	XX (XX)	XX (XX)

†Listing of specific reason will be provided

2) Important Protocol Deviations:

Type of Protocol Deviation	Xilonix+BSC (n=XXX)	Placebo+BSC (XXX)
	n (%)	n (%)
Deviation Category, n(%)	XX (XX)	XX (XX)

3) Enrollment at Clinical Site by Country:

Country	Site Number	Number of Patients Enrolled
XXXX	XXXX	X
	XXXX	X

4) Patient Demographic and Baseline Characteristics

	Treatment Group		Total (N= XXX)
	Xilonix+BSC (N= XXX)	Placebo+BSC (N=XXX)	
Age, year			
Mean	XX±XX	XX±XX	XX±XX
Median	XX	XX	XX
Min-Max	XX-XX	XX-XX	XX-XX
Age distribution, n(%)			
<65 years	XXX (XX%)	XXX (XX%)	XXX (XX%)
≥65 to <75 years	XXX (XX%)	XXX (XX%)	XXX (XX%)
>75 years	XXX (XX%)	XXX (XX%)	XXX (XX%)
Sex, n(%)			
Female	XX (XX)	XX (XX)	XX (XX)
*Race, n(%)			
White	XX (XX)	XX (XX)	XX (XX)
Black	XX (XX)	XX (XX)	XX (XX)
Asian	XX (XX)	XX (XX)	XX (XX)
Geographic Region , n(%)			
XXXX	XX (XX)	XX (XX)	XX (XX)
XXXX	XX (XX)	XX (XX)	XX (XX)
*KRAS Mutation Status, n(%)			
KRAS Mutation	XX (XX)	XX (XX)	XX (XX)
KRAS wild-type	XX (XX)	XX (XX)	XX (XX)
Test Not Done	XX (XX)	XX (XX)	XX (XX)
ECOG Performance Status			
0	XX (XX)	XX (XX)	XX (XX)
1	XX (XX)	XX (XX)	XX (XX)
2	XX (XX)	XX (XX)	XX (XX)
Baseline Weight, kg			
Mean	XX±XX	XX±XX	XX±XX
Median	XX	XX	XX
Min-Max	XX-XX	XX-XX	XX-XX
Histology, n(%)			
Adenocarcinoma	XX (XX)	XX (XX)	XX (XX)
Adenocarcinoma in situ	XX (XX)	XX (XX)	XX (XX)
Other	XX (XX)	XX (XX)	XX (XX)
Prior Therapies, n(%)			

XBiotech USA, Inc., Protocol 2012-PT023 V3.6

Interim Analysis #X, Data Date: ddmmyyyy

	Treatment Group		Total (N= XXX)
	Xilonix+BSC (N= XXX)	Placebo+BSC (N=XXX)	
XXX	XX (XX)	XX (XX)	XX (XX)
XXX	XX (XX)	XX (XX)	XX (XX)
Number of prior chemotherapy regimens, n(%)			
2	XX (XX)	XX (XX)	XX (XX)
3	XX (XX)	XX (XX)	XX (XX)
4	XX (XX)	XX (XX)	XX (XX)
5	XX (XX)	XX (XX)	XX (XX)
≥6	XX (XX)	XX (XX)	XX (XX)

5) Exposure by Treatment Groups

	Xilonix+BSC (N=XXX)			Placebo+BSC (N=XXX)		
	N	Mean±SD	Median (IQR)	N	Mean±SD	Median (IQR)
All Subjects	XXX	XX±XX	XX-XX	XXX	XX±XX	XX-XX
Female	XXX	XX±XX	XX-XX	XXX	XX±XX	XX-XX
Male	XXX	XX±XX	XX-XX	XXX	XX±XX	XX-XX
Age group=<65yr	XXX	XX±XX	XX-XX	XXX	XX±XX	XX-XX
Age group=65-75yr	XXX	XX±XX	XX-XX	XXX	XX±XX	XX-XX
Age group=>75yr	XXX	XX±XX	XX-XX	XXX	XX±XX	XX-XX

6) Clinical Response Rate by Treatment Groups ITT Population:

	Xilonix+BSC	Placebo+BSC
N	XXX	XXX
Clinical Response, n (% , 95% CI)	XX (XX, XX-XX)	XX (XX, XX-XX)
Difference (effect size)	XX%	
P value from Pearson Chi-Square test (one-tailed)	0.01	
Relative Risk (95% CI)	X.XX (X.XX to X.XX)	

7) Clinical Response Rate by Treatment Groups PP Population:

XBiotech USA, Inc., Protocol 2012-PT023 V3.6

Interim Analysis #X, Data Date: ddmmmyyyy

	Xilonix+BSC	Placebo+BSC
N	XXX	XXX
Clinical Response, n (% , 95% CI)	XX (XX, XX-XX)	XX (XX, XX-XX)
Difference (effect size)	XX%	
P value from Pearson Chi-Square test (one-tailed)	0.01	
Relative Risk (95% CI)	X.XX (X.XX to X.XX)	

8) Objective Response Rate by Treatment Groups ITT Population:

	Xilonix+BSC	Placebo+BSC
N	XXX	XXX
Objective Response, n (% , 95% CI)	XX (XX, XX-XX)	XX (XX, XX-XX)
Difference (effect size)	XX%	
P value from Pearson Chi-Square test (one-tailed)	0.01	
Relative Risk (95% CI)	X.XX (X.XX to X.XX)	

9) Objective Response Rate by Treatment Groups PP Population:

	Xilonix+BSC	Placebo+BSC
N	XXX	XXX
Objective Response, n (% , 95% CI)	XX (XX, XX-XX)	XX (XX, XX-XX)
Difference (effect size)	XX%	
P value from Pearson Chi-Square test (one-tailed)	0.01	
Relative Risk (95% CI)	X.XX (X.XX to X.XX)	

10) Disease Control Rate by Treatment Groups ITT Population:

	Xilonix+BSC	Placebo+BSC
--	-------------	-------------

XBiotech USA, Inc., Protocol 2012-PT023 V3.6

Interim Analysis #X, Data Date: ddmmyyyy

N	XXX	XXX
Disease Control Rate, n (% , 95% CI)	XX (XX, XX-XX)	XX (XX, XX-XX)
Difference (effect size)	XX%	
P value from Pearson Chi-Square test (one-tailed)	0.01	
Relative Risk (95% CI)	X.XX (X.XX to X.XX)	

11) Disease Control Rate by Treatment Groups PP Population:

	Xilonix+BSC	Placebo+BSC
N	XXX	XXX
Disease Control Rate, n (% , 95% CI)	XX (XX, XX-XX)	XX (XX, XX-XX)
Difference (effect size)	XX%	
P value from Pearson Chi-Square test (one-tailed)	0.01	
Relative Risk (95% CI)	X.XX (X.XX to X.XX)	

12) Secondary Endpoints Results: Change from Baseline

	Placebo+BSC (n= xxx)			Xilonix+BSC (n= xxx)			P*
	Baseline Mean (95% CI)	Follow-up Mean (95% CI)	Change LS Mean±SE	Baseline Mean (95% CI)	Follow-up Mean (95% CI)	Change LS Mean±SE	
Platelet, 1000/cu mm	XXX±XXX	XXX±XXX	X.XX±X.XX	XXX±XXX	XXX±XXX	X.XX±X.XX	0.XXX
PRO: Global QOL Score	XXX±XXX	XXX±XXX	X.XX±X.XX	XXX±XXX	XXX±XXX	X.XX±X.XX	0.XXX
PRO Symptom Score: Pain	XXX±XXX	XXX±XXX	X.XX±X.XX	XXX±XXX	XXX±XXX	X.XX±X.XX	0.XXX
PRO Symptom Score: Fatigue	XXX±XXX	XXX±XXX	X.XX±X.XX	XXX±XXX	XXX±XXX	X.XX±X.XX	0.XXX
PRO Symptom Score: Appetite	XXX±XXX	XXX±XXX	X.XX±X.XX	XXX±XXX	XXX±XXX	X.XX±X.XX	0.XXX
Lean Body Mass, kg	XXX±XXX	XXX±XXX	X.XX±X.XX	XXX±XXX	XXX±XXX	X.XX±X.XX	0.XXX

13) All Adverse Events by CTCAE Grade

XBiotech USA, Inc., Protocol 2012-PT023 V3.6

Interim Analysis #X, Data Date: ddmmyyyy

Body System or Organ Class		Group: Xilonix+BCS (N=XXX) Statistics n (%)					Group: Placebo+BCS (N= XX) Statistics n (%)				
		Grade I/II	Grade III	Grade IV	Grade V	Total	Grade I/II	Grade III	Grade IV	Grade V	Total
	AE Preferred Term	XX (XX.X%)	XX (XX.X%)	XX (XX.X%)	XX (XX.X%)	XX (XX.X%)	XX (XX.X%)	XX (XX.X%)	XX (XX.X%)	XX (XX.X%)	XX (XX.X%)
XXXXXX		XX (XX.X%)	XX (XX.X%)	XX (XX.X%)	XX (XX.X%)	XX (XX.X%)	XX (XX.X%)	XX (XX.X%)	XX (XX.X%)	XX (XX.X%)	XX (XX.X%)
	XXXXXX	XX (XX.X%)	XX (XX.X%)	XX (XX.X%)	XX (XX.X%)	XX (XX.X%)	XX (XX.X%)	XX (XX.X%)	XX (XX.X%)	XX (XX.X%)	XX (XX.X%)
	XXXXXX	XX (XX.X%)	XX (XX.X%)	XX (XX.X%)	XX (XX.X%)	XX (XX.X%)	XX (XX.X%)	XX (XX.X%)	XX (XX.X%)	XX (XX.X%)	XX (XX.X%)
	XXXXXX	XX (XX.X%)	XX (XX.X%)	XX (XX.X%)	XX (XX.X%)	XX (XX.X%)	XX (XX.X%)	XX (XX.X%)	XX (XX.X%)	XX (XX.X%)	XX (XX.X%)

The above table will be provided for SAEs.

14) Drug-related AEs

[figure not shown]
Body System or Organ Class		Group: Xilonix+BCS; Related (N=XX) Statistics n (%)					Group: Xilonix+BCS; Not Related (N=XX) Statistics n (%)				
		Grade I/II	Grade III	Grade IV	Grade V	Total	Grade I/II	Grade III	Grade IV	Grade V	Total
	AE Preferred Term	XX (XX.X%)	XX (XX.X%)	XX (XX.X%)	XX (XX.X%)	XX (XX.X%)	XX (XX.X%)	XX (XX.X%)	XX (XX.X%)	XX (XX.X%)	XX (XX.X%)
XXXXXX		XX (XX.X%)	XX (XX.X%)	XX (XX.X%)	XX (XX.X%)	XX (XX.X%)	XX (XX.X%)	XX (XX.X%)	XX (XX.X%)	XX (XX.X%)	XX (XX.X%)
	XXXXXX	XX (XX.X%)	XX (XX.X%)	XX (XX.X%)	XX (XX.X%)	XX (XX.X%)	XX (XX.X%)	XX (XX.X%)	XX (XX.X%)	XX (XX.X%)	XX (XX.X%)

15) AEs by Age Group:

Body System or Organ Class		Group: Xilonix+BCS; Under 65 year; (N=88) Statistics n (%)					Group: Xilonix+BCS; 65 to 75 year; (N=56) Statistics n (%)					Group: Xilonix+BCS; Over 75 year; (N=15) Statistics n (%)				
		Grade I/II	Grade III	Grade IV	Grade V	Total	Grade I/II	Grade III	Grade IV	Grade V	Total	Grade I/II	Grade III	Grade IV	Grade V	Total
	AE Preferred Term	XX (XX.X%)	XX (XX.X%)	XX (XX.X%)	XX (XX.X%)	XX (XX.X%)	XX (XX.X%)	XX (XX.X%)	XX (XX.X%)	XX (XX.X%)	XX (XX.X%)	XX (XX.X%)	XX (XX.X%)	XX (XX.X%)	XX (XX.X%)	XX (XX.X%)
XXXXXX		XX (XX.X%)	XX (XX.X%)	XX (XX.X%)	XX (XX.X%)	XX (XX.X%)	XX (XX.X%)	XX (XX.X%)	XX (XX.X%)	XX (XX.X%)	XX (XX.X%)	XX (XX.X%)	XX (XX.X%)	XX (XX.X%)	XX (XX.X%)	XX (XX.X%)
	XXXXX	XX (XX.X%)	XX (XX.X%)	XX (XX.X%)	XX (XX.X%)	XX (XX.X%)	XX (XX.X%)	XX (XX.X%)	XX (XX.X%)	XX (XX.X%)	XX (XX.X%)	XX (XX.X%)	XX (XX.X%)	XX (XX.X%)	XX (XX.X%)	XX (XX.X%)

16) Table and Figure for Progression-free Survival:

Kaplan-Meier Curves Comparing Progression-free Survival

[figure not shown]
Summary Table of Kaplan-Meier Log-Rank Test

Stratum	Total subjects	Failed	Censored	Percent Censored	25 th %ile	50 th %ile	75 th %ile
					95% CI	95% CI	95% CI
Xilonix	XX	XX	XX	XX.X%	XX.X (X.X, X.X)	XX.X (X.X, X.X)	XX.X (X.X, X.X)
Placebo	XX	XX	XX	XX.X%	XX.X (X.X, X.X)	XX.X (X.X, X.X)	XX.X (X.X, X.X)
Log-rank test		$\chi^2=XX$ (SE= XX)	P=0.XXX				

XBiotech USA, Inc.
Protocol 2012-PT023 V3.6; Interim Analysis #X
Data Date: ddmmyyyy

TABLES AND FIGURES FOR OVERALL SURVIVAL ANALYSIS

Summary Figure of Kaplan-Meier Curves of Overall Survival by Treatment Group

XBiotech USA, Inc.
 Protocol 2012-PT023 V3.6; Interim Analysis #X
 Data Date: ddmmyyyy

Page X of Y

Summary Table of Kaplan-Meier Event Summary, by Treatment Group

Survival Time (months)	Xilonix (N=XX)					Placebo (N=XX)				
	Survival Prob	Survival Standard Error	Number Failed	Number Remaining on Therapy	Survival Prob	Survival Standard Error	Number Failed	Number Remaining on Therapy		
0.0	0.XXX	0.XXX	XX	XX	0.XXX	0.XXX	XX	XX		
6.0	0.XXX	0.XXX	XX	XX	0.XXX	0.XXX	XX	XX		
12.0	0.XXX	0.XXX	XX	XX	0.XXX	0.XXX	XX	XX		
18.0	0.XXX	0.XXX	XX	XX	0.XXX	0.XXX	XX	XX		

XBiotech USA, Inc.
 Protocol 2012-PT023 V3.6; Interim Analysis #X
 Data Date: ddmmyyyy

Page X of Y

Summary Table of Kaplan-Meier Log-Rank Test

Stratum	Total subjects	Failed	Censored	Percent Censored	25 th %ile 95% CI	50 th %ile 95% CI	75 th %ile 95% CI
Xilonix	XX	XX	XX	XX.X%	(X.X, X.X)	(X.X, X.X)	(X.X, X.X)
Placebo	XX	XX	XX	XX.X%	(X.X, X.X)	(X.X, X.X)	(X.X, X.X)
Log-rank test		$\chi^2=XX$ (SE= XX)	P=0.XXX				

XBiotech USA, Inc.
 Protocol 2012-PT023 V3.6; Interim Analysis #X
 Data Date: ddmmyyyy

[figure not shown]
Summary Table of Group Sequential Boundary and Interim Analysis Results

Stage	Information Level		Score Scale				p-value scale			Action*
	Proportion	Actual	Futility Boundary	Efficacy Boundary	Estimate	Futility Boundary	Efficacy Boundary	Estimate		
1	50%	XX.X%	X.XX	X.XX	X.XX	0.XXXX	0.XXXX	0.XXXX	XXXXXX	
2	75%	XX.X%	X.XX	X.XX	X.XX	0.XXXX	0.XXXX	0.XXXX	XXXXXX	
3	100%	XX.X%	X.XX	X.XX	X.XX	0.XXXX	0.XXXX	0.XXXX	XXXXXX	

*Continue; Stop for Futility; or Stop for Efficacy

Xbiotech USA, Inc.
Protocol 2012-PT023 V3.6; Interim Analysis #X
Data Date: ddmmmyyy

Page X of Y

XBiotech USA, Inc.
 Protocol 2012-PT023 V3.6; Interim Analysis #X
 Data Date: ddmmyyyy

Listing of Subject Disposition / Survival

Subject ID	Sex	Age (years)	Treatment Group	Status*	Discontinuation Reason	Time to Status
1	M/F	X.XX	X.XX	XXXXXXXXXXXX	XXXXXXXXXXXX	XXXXXX
2	M/F	X.XX	X.XX	XXXXXXXXXXXX	XXXXXXXXXXXX	XXXXXX
3	M/F	X.XX	X.XX	XXXXXXXXXXXX	XXXXXXXXXXXX	XXXXXX

*Never Dosed; On Study; Discontinued - Death; Discontinued - Other

Programming Notes:

Please sort by Subject ID

For Status = Discontinued, Please add in if the subject discontinued due to death, or for any other reason

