New agents that control disease progression—while improving tumor-related symptoms, rather than causing significant therapy related morbidity—are vitally needed to treat patients with advanced cancer, including those with colorectal cancer. An approach has been taken to develop such an agent using a monoclonal antibody to block the chronic inflammation involved in both malignant disease progression and constitutional symptoms.

Xilonix™ is expected to inhibit tumor growth and metastasis by interrupting crucial signals that drive angiogenesis and invasiveness. The antibody therapy may also block tumor microenvironment infiltration by leukocytes (such as myeloid suppressor cells) that suppress antitumor immunity, enabling better host immune control of the disease. In addition to local effects on the tumor, Xilonix™ is expected to work systemically to correct the metabolic dysregulation, fatigue and anxiety mediated by chronic inflammatory signaling to the central nervous system. The use of this antibody monotherapy to target chronic inflammation is proposed as a safe, effective treatment for patients with metastatic colorectal cancer.

2 Study Design

This is a phase III, multicenter, double blind, randomized, placebo controlled pivotal trial of the True Human monoclonal antibody MABp1 in subjects with metastatic colorectal cancer who are refractory to standard therapy.

- Enrolled subjects will be randomized (2:1) to receive either MABp1 plus best supportive care (BSC) or placebo plus BSC.
- BSC is defined as those measures intended to provide palliation of symptoms and improve quality of life. This includes, but is not limited to, antibiotics, anti-emetics, narcotics, and parenteral nutrition.
- Subjects randomized to MABp1 or placebo will receive the study drug via intravenous infusion once every 2 weeks (one cycle).

3 Study Endpoints:

3.1 Primary Efficacy Endpoint:

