EORTC: Longitudinal and descriptive analysis will be performed to assess patient reported outcomes (PRO). The EORTC survey results will be converted to domain specific scores using the prescribed algorithm (Appendix A). Scores on the EORTC QLQ-C30 functional and symptom scales will be summarized according to the randomization groups. The EORTC survey responses will be converted to domain specific scores using the prescribed algorithm. Scores on EORTC QLQ-C30 functional and symptom scales will be summarized according to the randomization groups. Descriptive statistics of PRO score will be summarized by treatment group.

Patients showing stabilization or improvement from baseline (≤ 0 change) on any two of the three symptom scales (pain, fatigue, appetite loss) will be considered EORTC responders. Patients experiencing reduction or worsening on the symptom scales will be defined as non-responders. Patients missing the follow-up assessment will be considered non-responders. The comparison of responder rate and absolute change will be performed similar to as described for LBM.

Clinical Response Rate: Patients responding on LBM (≥ 0 kg change from baseline) and EORTC (≤ 0 change on any two three symptoms) will be considered Clinical Responders. Patients missing follow-up status will be considered non-responders. Clinical Response Rate will be compared using a Pearson chi-square test. Proportion by treatment groups and relative risk estimates will be presented with CMH 95% confidence intervals.

Platelet Count: Change in platelet count from baseline to follow-up will be compared between treatment groups using the ANCOVA method described above. The last visit cycle where at least 20 patients per group are on study will be used for follow-up data cut-off for this measure. Trend line plots displaying the median platelet count over time (visit cycles) by treatment groups will be generated.

Progression Free Survival (PFS): PFS will be compared by Kaplan-Meier method using log-rank test. Kaplan-Meier plots by treatment arm will be produced, and point estimates and 95% CIs will be summarized.

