Exposure duration will be summarized by treatment groups and presented in a table format. Exposure duration will be calculated as Last infusion date – C1D1 infusion date.

Adverse events will be grouped by System Organ Class (SOC) and Preferred Term (PT) within SOC according MedDRA coding dictionary (version 18.0). The number of subjects reporting at

least one adverse event by PT will be summarized across treatment groups. AEs will be summarized by SOC and PT, by relatedness to study treatment and age group. Tables summarizing PT by CTCAE grade and narratives for serious adverse events (SAE) will be presented for each treatment group. A listing of all adverse events by treatment group will be included in the appendix section.

The numbers and percentages of patients experiencing any adverse event (AE) and any serious adverse event (SAE) will be summarized per treatment group will be compared using Chi-square test. The numbers and percentages of patients experiencing any adverse events will also be summarized by maximum severity and relatedness to study treatment per treatment group. Clinical laboratory tests (hematology and chemistry) data will be listed for each subject. Laboratory data will be summarized by Xilonix™ and placebo group. Values outside the normal reference range will be flagged as high or low on the listings. Summary statistics for baseline, on-treatment and change from baseline values will be provided by treatment group in table format. Statistical process control charts showing baseline and post-baseline visit values in comparison with laboratory reference values will be provided for tests of interest.

Vital signs listings (include temperature, pulse, and blood pressure) for each subject will be provided in the appendix section of the Clinical Study Report. Summary statistics by treatment groups will be presented in tabular format.

9 List of Planned Tables

- Randomization by study site, stratified by country
- Subject disposition (all enrolled subjects) with reason for discontinuation, cumulative dose (for Xilonix™ group), and duration on study before discontinuation, broken down by treatment group
- Major protocol deviations (all enrolled subjects)
- Baseline demographic and clinical characteristics by treatment group (per-protocol population)
- Baseline demographic and clinical characteristics by treatment group (ITT population)
- Baseline laboratory data by treatment group (per-protocol population)

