- Baseline laboratory data by treatment group (ITT population)
- Listing of patients excluded from efficacy analysis, with reason for exclusion
- Primary endpoint (overall survival) summary by treatment group (count and percent, median survival) (ITT and PP population)
- Secondary endpoints (LBM, platelet count, and EORTC score): summary of change by treatment group: baseline, follow-up, and change with confidence intervals (ITT population and PP population).
- SAE by treatment group (all randomized patients)
- Adverse events (counts, percent) by MedDRA preferred term by treatment group
- Detail listing of adverse events by treatment group (all randomized patients)
- Summary of vital signs and change from baseline over visits (all randomized patients)

- Exploratory summary on pharmacodynamics (PK) analysis findings (patients in Xilonix arm)
- Exploratory summary on Clinical Response Rate analysis findings (patients in Xilonix arm)

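### SAP table shells 14 (drug-related AEs) and 15 (AEs by age group) have Xilonix columns only, so these two safety breakdowns have no placebo benchmark

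*SAP*

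**What the plan says.** The trial is a placebo-controlled comparison: "Enrolled subjects will be randomized (2:1) to receive either MABp1 plus best supportive care (BSC) or placebo plus BSC" (SAP section 2).

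- **Shell 14, Drug-related AEs.** There are two column blocks, "Group: Xilonix+BCS; Related (N=XX) Statistics n" and "Group: Xilonix+BCS; Not Related (N=XX) Statistics n".
- **Shell 15, AEs by Age Group.** There are three column blocks, starting with "Group: Xilonix+BCS; Under 65 year; (N=88) Statistics n". The other two are also Xilonix, with printed sizes of 56 and 15.
- **Shell 13, All AEs by CTCAE Grade.** This shell does carry a placebo block, "Group: Placebo+BCS (N= XX) Statistics n", and a note says that it is to be repeated for SAEs. No such note follows shell 14 or 15.
- **SAP 8.4.2, Analysis of Safety Outcomes.** Patients with any AE are to be "summarized by maximum severity and relatedness to study treatment per treatment group". A separate sentence plans organ-class and preferred-term summaries by relatedness and by age group without naming the arms.
- **Clinical response.** The list in SAP section 9 reads "Exploratory summary on Clinical Response Rate analysis findings (patients in Xilonix arm". SAP 8.4.2, Secondary Effectiveness Endpoints, plans a chi-square comparison and says: "Proportion by treatment groups and relative risk estimates will be presented with CMH 95% confidence intervals".

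**The concern.** Under Protocol 9.5 the investigator assigns causality. Under Protocol 5.3 investigators stay blinded until all patients have completed and the database is locked, emergencies aside. Placebo patients will therefore also have events judged related to study drug. In refractory metastatic colorectal cancer many disease symptoms are open to such attribution. The share of placebo patients with a given term judged related shows how much of the Xilonix figure is background.

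Shell 14 instead sets related against not-related events within the Xilonix arm. That is not the randomised contrast, and it cannot separate background attribution from drug effect for any single term. Shell 15 has the same weakness for age: a higher rate in older Xilonix patients could reflect age or disease as easily as drug.

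The sponsor already reasons from the placebo comparison. Protocol 8.2 removes four terms from the expected reactions because a placebo-controlled trial showed no difference between groups. Protocol 8.1 looks to a randomised trial to settle whether proteinuria is a consequence of treatment. A one-arm table of related events cannot support that kind of argument.

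**Working it through.** The plan states no figure to reproduce, so the check is a side-by-side reading of shells and text.

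**1. Count the placebo blocks in each shell.**

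| Shell | Content | Column blocks | Placebo blocks |
|---|---|---|---|
| 5 | Exposure, overall and by sex and age band | 2 | 1 |
| 6, 7 | Clinical response (ITT, PP) | 2 each | 1 each |
| 13 | All AEs by grade, repeated for SAEs | 2 | 1 |
| 14 | Related and not-related AEs | 2 | 0 |
| 15 | AEs by age group | 3 | 0 |

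Shell 5 uses essentially the same three age bands as shell 15 and shows both arms, so shell 15 departs from the SAP's own layout.

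**2. Compare shell 14 with the text.** The safety section wants patients with any AE broken down by relatedness for each treatment group. Shell 14 is the only shell that shows relatedness, and it omits placebo. The text therefore asks for more than the shells deliver.

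**3. Compare shell 15 with the text.** The age-group sentence does not name the arms, so shell 15 does not contradict it. The sentence leaves the matter open and the shell settles it without placebo.

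**4. Check what is kept.** Shell 13 gives every AE by organ class, term and grade for both arms, and again for SAEs. The safety section also plans preferred-term counts across treatment groups, chi-square comparisons of any AE and any SAE, and AE listings by treatment group. For clinical response, shells 6 and 7 give both arms, the difference, a p value and a relative risk.

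**5. Printed group sizes.** Shell 15 carries 88 + 56 + 15 = 159 Xilonix patients, where comparable shells use placeholders. SAP section 5 plans 400 in that arm. The SAP does not say where the 159 come from.

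**The case against.** The strongest reply is that the text governs and the shells only illustrate. SAP 5.1 describes the appended shells as being for interim analysis, and their page headers say the same. The safety text already promises an any-AE relatedness summary for each arm. The all-causality comparison does not depend on anyone's attribution, so an excess of events on Xilonix would show in shell 13. The age sentence names no arms, so a placebo column there could be called a preference.

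Most of this stands, and it rules out three stronger readings that a reader might infer:

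- **That a true excess of adverse events would be invisible.** Shell 13 and the chi-square tests compare both arms.
- **That no placebo rate of related events is planned.** The any-AE summary by relatedness is specified per treatment group.
- **That the clinical response comparison is lost.** The analysis text and shells 6 and 7 keep it for ITT and PP. The section 9 entry is a misworded line.

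The reply does not dispose of the gap itself. No text or shell requires related events by preferred term and grade, or events by age group, for placebo. Programmers work from shells. Interim status does not remove the point either, because SAP section 4 has the IDMC watching for early treatment harm and tables in this layout could reach it.

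**Conclusion.** The point holds in a limited form. Shells 14 and 15 leave out the placebo breakdown of related events by preferred term and grade, and of events by age group. Shell 14 also falls short of the SAP's own call for relatedness by arm. The effect is on the interpretability of two safety tables. Nothing changes in the primary survival analysis, alpha, power or the overall safety comparison.

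No patient count can be attached, because the documents give no expected rate of AEs judged related in either arm.

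The conclusion assumes that the readable text of the shells is complete. A figure is missing beside shell 14, and a placebo version could have been lost there, although nothing in the text points to one. It also assumes that relatedness is recorded alike in both arms, which the blinding and the causality section of the protocol support.

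**What to change.** 1. Add Placebo+BSC blocks to shell 14 (related and not related) and shell 15 (each age band).
2. Use each arm's Safety Population as denominator, by treatment received, as defined in SAP 7.1, and show percentages, since 2:1 allocation makes raw counts non-comparable. SAP 8.4.2, Analysis of Safety Outcomes, says that all randomised subjects enter the safety analysis. State one denominator in both places.
3. In that section, add *by treatment group* to the sentence on organ-class and preferred-term summaries by relatedness and age group.
4. Housekeeping: replace the printed 88, 56 and 15 in shell 15 with placeholders, and change the qualifier on the clinical response entry in SAP section 9 from the Xilonix arm to *by treatment group (ITT and PP)*.

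The cost is a short SAP edit and table programming. No new data, visits or assessments are needed.
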